## **Randomization and Blinding**

After consent was obtained, participants were screened to determine eligibility. After participants were determined to be eligible, they were randomized with equal probability to receive either Pirfenidone or placebo in a double-blinded fashion. Treatment assignment slots were not re-used; each consecutive randomized participant received the next consecutive unused treatment assignment slot. Randomization was stratified by center with random block sizes. The password protected computer text file that contained the translation of treatment labels A and B to either Pirfenidone or placebo was maintained by the unblinded DCC statistician. Details will be provided in the final study report.

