### **Multi-center Studies**

In this multi-center clinical trial, to allow for center-specific effect sizes, center will serve as a random effect in all primary analyses comparing treatment arms. Model fitting problems from sparse data may be encountered since enrolment stopped early due to COVID-19. If that occurs, then network (US, Canada, UK, Australia) will serve as random effect. As exploratory analyses, results within center or network will be described.

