## **Efficacy Analyses**

All efficacy variables will be listed by participant within study center. Data will be summarized by treatment arm using descriptive statistics (N, Mean, Standard Deviation, Minimum, and Maximum) for continuous efficacy variables. Number and percent will be presented for categorical efficacy variables. Columns will be Placebo and Pirfenidone. The primary efficacy population will be the ITT population, where all randomized participants are included according to their randomized treatment arm.

The primary efficacy analysis for this trial has a binary composite outcome. (A) Patients will be

categorized based on their decline since baseline in percent predicted FVC of 10% or greater during study period. (B) Patients will also be categorized based on death during study period. The composite primary endpoint is the occurrence of either (A) or (B) during the study period. Comparisons between treatment arms will be performed using a mixed effect logistic regression model, adjusting for the continuous fixed covariate baseline percent predicted FVC and the fixed binary covariate HRCT pattern. Treatment arm will be an independent fixed effect and study center will be a random effect in the analysis (Kahn, 2014). The likelihood-ratio test will be used to test for differences between treatment arms. Treatment arm will be tested at a 2-sided 5% significance level. The components of the primary endpoint will be similarly analyzed.

The adjusted odd ratios together with 95% confidence interval and p-value will be used to quantify the effect of treatment, comparing pirfenidone with placebo as the reference. The data will be coded such that an odds ratio less than 1.0 will indicate that pirfenidone is protective. Assumptions for models will be assessed by examining the plots for the residual values. If data sparseness causes model fitting problems, the model will be simplified by using study network instead of study center as a random effect and/or eliminating the random center (or network) effect.

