The longitudinal continuous efficacy endpoints will be presented graphically and numerically. The analysis will use a restricted maximum likelihood-based repeated measures approach with a random slope and intercept model. Visit will be analyzed as weeks since baseline. The analysis will include the fixed, categorical effect of treatment arm, fixed continuous effect of visit, and the treatment arm-by-visit interaction. The baseline value will be included as a fixed covariate. Random effects will be included for participant response and for both visit and intercept. An unstructured covariance structure will be used to model the within-participant errors. If this analysis fails to converge, the other structures that will be tested will include spatial power because visits are unevenly spaced, and compound symmetry. The covariance structure converging to the best fit, as determined by Akaike's information criterion, will be used as the

primary analysis. The Kenward-Roger approximation will be used to estimate denominator degrees of freedom and adjust standard errors. The analysis will use all measurements obtained over the 52-week study period, including those from patients who had discontinued study medication. The model allows for missing data assuming missing at random. If model optimization does not converge, then the random effect will be removed. Significance tests will be based on least squares means using a two-sided  $\alpha = 0.05$  with two-sided 95% confidence interval. The primary treatment comparison of slopes will be assessed through the treatment-by-visit interaction coefficient. Assumptions for models will be assessed by examining plots of the residual values.

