Analyses of time-to-event outcomes will be performed using mixed effect proportional hazards regression modelling with treatment arm as main effect, and with study center as random effect. The analysis will include the fixed categorical effects of treatment arm and baseline HRCT pattern category. For time-to-event analyses involving spirometry, the baseline value will also be a covariate. The censoring date will be the earlier of the end of study period date or the date the participant was last observed without the event. The actual dates, rather than visit number will be used to calculate time to event, and time will be expressed in weeks. The proportional hazards assumption will be assessed using Kaplan Meier plots and Schoenfeld residuals. A time dependent covariate will be added if proportionality is not supported. The treatment arm difference will be tested at the 2-sided 5% significance level. The adjusted hazard ratio and 95% confidence interval for the hazard ratio will be reported. The data will be coded such that for death and for endpoints that indicate a decline in function, a hazard ratio less than 1.0 will indicate that pirfenidone is protective. Breslow's method for handling ties will be used.

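### The SAP's longitudinal model omits center, the randomization stratum, and HRCT pattern, the one pre-specified covariate, although the primary and time-to-event models include both

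*SAP*

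**What the plan says.** The SAP's Efficacy Analyses section sets out three models.

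- **Primary binary endpoint.** A mixed logistic model, "adjusting for the continuous fixed covariate baseline percent predicted FVC and the fixed binary covariate HRCT pattern". On center: "Treatment arm will be an independent fixed effect and study center will be a random effect in the analysis". If data are sparse, network may replace center, or the random effect may be dropped.
- **Longitudinal continuous endpoints.** "The analysis will include the fixed, categorical effect of treatment arm, fixed continuous effect of visit, and the treatment arm-by-visit interaction". Then "The baseline value will be included as a fixed covariate", and "Random effects will be included for participant response and for both visit and intercept". The slope comparison is the arm-by-visit coefficient, tested at two-sided 0.05.
- **Time-to-event endpoints.** A mixed proportional hazards model with a random center effect. "The analysis will include the fixed categorical effects of treatment arm and baseline HRCT pattern category".

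Three other statements bear on the choice of terms. Under Randomization and Blinding: "Randomization was stratified by center with random block sizes". Under Multi-center Studies: "center will serve as a random effect in all primary analyses comparing treatment arms". Under Covariates, pre-specified covariates enter the primary analyses, and the only one named is HRCT pattern, UIP-like versus other.

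**The concern.** Two of the three efficacy models carry the stratification factor and the one covariate chosen as prognostic. The third, which serves the FVC slopes, carries neither, and no reason is given.

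Restricting the general rules to the primary endpoint does not explain the pattern. Time to FVC decline or death is a secondary endpoint (SAP, Secondary Endpoints, item 7), yet its model has both terms. The longitudinal paragraph also describes the covariance structure it selects as its primary analysis. One analyst could add center and HRCT pattern under the general rules while another leaves them out, and both could cite the SAP.

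Two things are at stake: some precision on the continuous lung-function results, in a trial that closed at 123 participants when 254 with complete data had been planned for, and a modelling choice that could still be open when the data are unblinded.

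**Working it through.** **1. Terms side by side.**

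| Model | Center | HRCT pattern | Baseline value |
|---|---|---|---|
| Primary logistic | random | fixed | percent predicted FVC |
| Longitudinal continuous | absent | absent | yes |
| Time-to-event | random | fixed | for spirometry endpoints |

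The SAP gives no power or variance figure for the longitudinal endpoints, so there is no figure of its own to reproduce. The steps below are illustrative.

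**2. Slope contrast.** From the documents: FVC at baseline and weeks 13, 26, 39 and 52. Assumed: slope SD 5 points per year, residual SD 3, complete visits, baseline placed at time 0, half of participants UIP-like, and 62 per arm (124 in all, against 123 randomized). With random intercept and slope and balanced visits,

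SE = √[2(σ²slope + σ²res/S)/n],

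where S is the sum of squared deviations of visit time in years. The intercept variance cancels.

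*Baseline also a response (five times).* S = 0.625 and σ²res/S = 9/0.625 = 14.4.
- Neither term: √[2(25 + 14.4)/62] = 1.127.
- HRCT main effect added: 1.127. It shifts level only, so nothing changes.
- HRCT-by-visit added: a 50:50 factor with slope difference d explains d²/4 of the slope variance.
  - d = 3: 2.25 of 25 (9%); SE = √[2(22.75 + 14.4)/62] = 1.095; variance ratio 39.4/37.15 = 1.06.
  - d = 4: 4 of 25 (16%); SE = √[2(21 + 14.4)/62] = 1.069; variance ratio 39.4/35.4 = 1.11.

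*Baseline a covariate only (four times).* S = 0.3125 and 9/0.3125 = 28.8.
- Neither term: √[2(25 + 28.8)/62] = 1.317.
- d = 3: √[2(22.75 + 28.8)/62] = 1.290; ratio 53.8/51.55 = 1.04.
- d = 4: √[2(21 + 28.8)/62] = 1.267; ratio 53.8/49.8 = 1.08.

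The gain is therefore 4% to 11% in variance terms, and nil if d = 0. The SAP does not say whether baseline is also a response.

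**3. Level contrasts.** Ignoring a factor that explains a share r of outcome variance inflates the variance by at most 1/(1 − r). At an assumed r = 0.05 this is 1/0.95 = 1.053, about 5%.

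**4. Type I error.** A null simulation of participant-level slopes used 123 participants, 33 sites, permuted blocks of 2 or 4 within site, a 50% HRCT split and 4,000 replicates. Block sizes and variance shares are assumed, and the adjusted analysis takes the variance components as known.

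| Share of slope variance (center, HRCT) | SE without both | SE with both |
|---|---|---|
| 0, 0 | 0.180 | 0.181 |
| 5%, 0 | 0.180 | 0.177 |
| 5%, 5% | 0.180 | 0.172 |
| 10%, 10% | 0.180 | 0.163 |

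The SE without the terms ranges from no larger to about 10% larger (0.180/0.163 = 1.10). Rejection rates were 3.9% to 5.0% without the terms and 4.8% to 5.5% with them (Monte Carlo error about 0.35 points). Because the simulation places both effects on the slope, its gains correspond to by-visit terms. A random center intercept would not deliver the center part of them.

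**The case against.** The strongest reply is that copying the other two models' terms into this one would do almost nothing for the slopes. That is correct: an HRCT main effect leaves the slope SE at 1.127, and a random center intercept likewise shifts level, not slope. The slope gain comes from HRCT-by-visit, a term in none of the SAP's models, and its size rests wholly on assumed inputs.

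A leaner model also has a case. With 123 participants over approximately 33 planned sites there are about 3.7 per site (123/33). The SAP itself expects fitting problems from sparse data, and the longitudinal model already carries random intercepts and slopes with an unstructured within-participant covariance. This supports having a fallback; it does not support silence about center. The protocol's earlier plan for continuous outcomes (10.4.2, Wilcoxon rank sum tests) also had no such adjustment, but the SAP has moved to a model that can take it.

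A reader might draw three stronger conclusions that the documents do not support.

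- *That disagreement between the three efficacy analyses could not be interpreted.* They report an odds ratio, a hazard ratio and a slope difference, which are not numerically comparable under any adjustment. In a linear model of a randomized trial, omitting a baseline covariate costs precision and does not change the treatment effect being estimated.
- *That the SAP breaks its own rule.* If primary analyses means the primary endpoint, nothing is breached. If it means the main analysis of each endpoint, the general sections already supply both terms. The text allows either.
- *That the model certainly governs FVC change and Dyspnea-12.* The SAP's endpoint definitions build these from the baseline value and the last value on study. Only the slope endpoints are clearly defined on all measurements. The wider reach is an inference from the phrase about longitudinal continuous endpoints and from the Missing Data section.

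**Conclusion.** The point holds as an unexplained omission with a possible cost in precision. The longitudinal model lacks the stratification factor and the only pre-specified covariate, both present in the other two efficacy models, and the general rules do not settle whether they apply.

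There is no bias, and the simulation showed no type I inflation; at most the test is mildly conservative. For level contrasts the cost is about 5% in variance at most if the omitted factor explains 5% of the outcome variance. For the slope contrast it is 4% to 11% under the assumed 3 to 4 point per year difference, slope SD 5 and residual SD 3, and zero if slopes do not differ by HRCT pattern. The documents give no variance components, so none of these figures is an estimate for this trial.

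Severity is minor to moderate: the SAP treats the secondary endpoints as hypothesis-generating (Multiple Testing).

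**What to change.** Before unblinding, amend the longitudinal paragraph of Efficacy Analyses to:

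1. add HRCT pattern and HRCT pattern-by-visit as fixed effects;
2. add center as a random effect, with the primary model's fallback to network, or to no center effect, if the model does not fit;
3. state which endpoints the model governs: the FVC slopes, FVC change, Dyspnea-12 and the other questionnaires.

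If the leaner model is preferred, say so and give the reason, and make clear in Covariates and Multi-center Studies that their rules do not reach it.

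The cost is a few sentences. Both variables are already in use in the other models, so no new data are needed. The downside is a somewhat larger model with a higher chance of needing the fallback.

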**Early Termination Visit**

Participants who terminate participation in the study (e.g. withdraw consent in writing, receive a lung transplant) will discontinue study treatment, cease all study procedures, and undergo the assessments listed below. These participants will also complete Visit 12/End of Study Phone Call 28 days after the last dose of study drug.

1. Review of AEs/SAEs, concomitant medications, oxygen use
2. Physical examination, resting oxygen saturation, vital signs, and weight
3. Clinical laboratory assessments, including hematology, serum chemistries, serologic tests, and blood pregnancy test for women of childbearing capacity
4. Biomarkers (See Appendix A)
5. Blood samples for genetic research (DNA PAXgene samples) - Optional
6. Spirometry (FVC, FEV1 without bronchodilator administration)
7. Lung volumes, DLCO or TLCO
8. Patient Reported Outcome Questionnaires (See Appendix A)
9. Study Medication Accountability, including collection of any unused study treatment
10. Study Medication Dosing review (participant diary)
11. HRCT scan

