### 17.3 MODIFICATIONS TO STUDY VISITS AND PROCEDURES

Conversion to remote study visits.

- Continued onsite visits **are not recommended or expected** at this time.
- Conversion to telehealth or video conferencing visits is acceptable as is contacting subjects by phone to conduct study visits. In most cases, local IRBs are accepting this conversion to remote visits without prior approval due to the urgent need to protect subjects.
- Efforts should be made to keep in contact with patients who are currently enrolled in the study through telemedicine and/or videoconferencing.

Schedule of Study Assessments edited for COVID-19.

- Visits 5 through 11 in the schedule of assessments can be converted to phone visits. There may be a reduction in the number of assessments, as not all will be feasible over the phone. If participants cannot be present for the visit, PFTs or Physical exam cannot be performed. The following assessments are categorized as the "expected assessments": Adverse events, Concomitant medication review, Supplemental oxygen review, Study medication dosing, Study medication accountability, Weight, Resting O2 Saturation, Patient questionnaire DAS 28 GH VAS, Patient GA, SGRQ, HAQ20, Dyspnea-12, LCQ, RAPID3, Vital status assessment.
- Monitoring of liver function testing should be continued as per protocol. If within the first 6 months of the study LFTs cannot be performed subjects should stop study treatment until labs can be obtained. Subjects are encouraged to continue the study visits.
- The subject is encouraged to restart study treatment when possible and appropriate.

- If the subject has interrupted study treatment for  $\geq 28$  days, a Pre-Restart Visit is required (Section 7.2.2). The Pre-Restart Visit will be conducted on the day study treatment is resumed. Subjects who restart study treatment will resume the visit schedule based on their date of randomization. If a regularly scheduled visit (Weeks 13, 26, 39, etc.) coincides with the Pre-Restart Visit, then the elements of the regularly scheduled visit as outlined above should be performed in lieu of the Pre-Restart Visit. Refer to Appendix B of the protocol on page 69 for re-titration.
- Visit window for visit 11 will be extended to +/- 4 weeks

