## **Study Assessments**

The schedule of all study assessments is in **Appendix A** of the protocol. Eligibility and randomization take place at Visit 2. Time windows for visits are below. There is an additional phone visit that occurs 28 days after the last study drug dose to assess vital status and adverse events.

Visit Number	Visit Week	Target Day of Visit	Visit Window
1	-8 to 0	-56 to 0	-56 to 0 days
2	0	1	0
3	1	7	± 2 days
4	2	14	± 2 days
5	4	28	± 1 week
6	8	56	± 1 week
7	13	91	± 2 weeks
8	19	133	± 1 week
9	26	182	± 2 weeks
10	39	273	± 2 weeks
11*	52	364	± 1 week

\* Visit 11 marks the end of the follow-up period. Protocol amendment V8 (US/CAN/AUS) /V10 (UK) extends the visit 11 window to ± 4 weeks due to COVID-19 laboratory closures.

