## **Primary and Secondary Endpoints and Relevant Variables**

*Composite endpoint of decline from baseline in percent predicted FVC of 10% or greater or death during study period.*

- FVC (percent predicted) at baseline
  - Last FVC (percent predicted) while on study
- Decline from baseline in percent predicted FVC is (last percent predicted FVC while on study) - (percent predicted FVC at baseline)
- Death (yes/no) while on study

*Decline from baseline in percent predicted FVC of 10% or greater during study period.*

- FVC (% predicted) at baseline
  - Last FVC (% predicted) while on study
- Decline from baseline in percent predicted FVC is (last percent predicted FVC while on study) - (percent predicted FVC at baseline)

*Frequency of progressive disease as defined by OMERACT: Relative decline from baseline in percent predicted FVC of  $\geq 10\%$ , or relative decline from baseline in percent predicted FVC  $\geq 5\%$  and  $< 10\%$ , and  $\geq 15\%$  relative decline from baseline in percent predicted DLCO (Khanna, Mittoo et al. 2015)*

- FVC (percent predicted) at baseline
  - Last FVC (percent predicted) while on study
- Relative decline from baseline in percent predicted FVC = [(Last FVC(percent predicted) – Baseline FVC (percent predicted))/Baseline FVC (percent predicted)]\*100
- DLCO (percent predicted) at baseline
  - Last DLCO (percent predicted) while on study

Relative decline in percent predicted DLCO = [(Last DLCO (percent predicted) – Baseline DLCO (percent predicted))/Baseline DLCO (percent predicted)]\*100

If DLCO (percent predicted) is missing, TLCO (percent predicted) will be substituted.

*Change from baseline over study period in FVC (L)*

- FVC (L) at baseline
- Last FVC (L) while on study

*Change from baseline over study period of percent predicted FVC*

- FVC (percent predicted) at baseline
- Last FVC (percent predicted) while on study

*Slope of percent predicted FVC over study period*

- All available percent predicted FVC measurements and dates while on study

*Slope of absolute FVC over study period*

- All available FVC measurements and dates while on study

*Time to decline of 10% or greater in percent predicted FVC at death over study period*

- Baseline percent predicted FVC and randomization date
- All measurements of percent predicted FVC while on study and date
- Death date, death indicator
- Last study visit date

*Proportion of participants with all-cause mortality*

- Death date present or absent

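### The SAP's FVC-slope model has redundant covariance parameters and its two responses to non-convergence have no stated order, so the final model is not fixed and some permitted endings may miss the 5% level

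*SAP*

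**What the plan says.** The SAP section Efficacy Analyses sets out one model for the longitudinal continuous endpoints. These include the slopes of percent predicted and absolute FVC (SAP secondary endpoints 5 and 6). The slope comparison is the arm-by-visit coefficient, with visit in weeks, tested at a two-sided 5% level with Kenward-Roger standard errors.

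- Random part: "Random effects will be included for participant response and for both visit and intercept".
- Residual part: "An unstructured covariance structure will be used to model the within-participant errors".
- First response to non-convergence: "If this analysis fails to converge, the other structures that will be tested will include spatial power" and compound symmetry, with AIC choosing among the structures that converge.
- Second response, later in the same paragraph: "If model optimization does not converge, then the random effect will be removed".

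On timing, the variable list for the percent predicted slope is "All available percent predicted FVC measurements and dates while on study", so actual dates are available. Visits will not fall exactly on nominal weeks: the SAP (Study Assessments) notes that an amendment "extends the visit 11 window to ± 4 weeks due to COVID-19 laboratory closures". Spirometry will also be incomplete. Protocol 17.3 allows remote visits and says "If participants cannot be present for the visit, PFTs or Physical exam cannot be performed", and the Early Termination Visit adds off-schedule tests ("Spirometry (FVC, FEV1 without bronchodilator administration").

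Protocol 10.4.2 plans a different slope analysis: a regression slope per participant, compared between arms by Wilcoxon rank sum test.

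**The concern.** A random intercept and slope and a free residual covariance matrix describe the same within-participant variation twice. A singular or non-converged fit is therefore possible, and the fallback wording may have to be used.

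That wording leaves several endings open. Two sentences respond to the same event without a stated order. The second refers to a single random effect although the model has more than one, and it names no residual structure to keep. The endings give different standard errors for the same slope difference. Where participants differ in their true rate of decline, an ending that omits this variation can understate the standard error. Kenward-Roger corrects for small samples, not for a wrong covariance structure.

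At stake are the p-values and intervals for two secondary endpoints that use all the spirometry in a trial that closed at 123 participants.

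**Working it through.** **Plan's own figure.** The documents give no sample size, power or variance for the slope analysis, only the nominal two-sided 5% level. The check is whether each ending holds it.

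**1. Identifiability.** Post-baseline spirometry is at weeks 13, 26, 39 and 52. A random intercept and slope has 3 parameters; an unstructured 4x4 residual matrix has 4 x 5 / 2 = 10. The table gives the rank of the Jacobian of V = ZGZ' + R. The actual-date case uses 123 participants with assumed timing variation of +/-2 weeks, and +/-4 weeks at week 52.

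| Residuals, with random intercept and slope | Parameters | Rank, nominal weeks | Rank, actual dates |
|---|---|---|---|
| Unstructured | 13 | 10 | 12 |
| Compound symmetry | 5 | 4 | 4 |
| Spatial power | 5 | 5 | 5 |
| Independent | 4 | 4 | 4 |

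At nominal weeks an unstructured R already spans everything that ZGZ' can add. With actual dates the intercept variance is still absorbed. Compound symmetry duplicates the random intercept. The slope contrast itself remains estimable.

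**2. Compound symmetry without a random slope, complete data.** Let tau be the SD of true slopes (points of percent predicted FVC per year) and sigma the residual SD. With time in years, 0.25, 0.5, 0.75 and 1, Sxx = 2(0.375^2) + 2(0.125^2) = 0.3125.

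- True variance of one participant's slope: tau^2 + sigma^2/Sxx
- Variance the model assumes: sigma^2/Sxx + tau^2/3
- SE ratio = sqrt(assumed / true); true error = 2[1 - Phi(1.96 x SE ratio)]

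For tau = sigma = 3: assumed 28.8 + 3 = 31.8, true 28.8 + 9 = 37.8, ratio sqrt(0.841) = 0.917, error 7.2%.

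| tau / sigma (assumed) | SE ratio | True error |
|---|---|---|
| 0 / 3 | 1.000 | 5.0% |
| 3 / 3 | 0.917 | 7.2% |
| 4 / 3 | 0.873 | 8.7% |
| 6 / 3 | 0.793 | 12.0% |
| 6 / 2 | 0.713 | 16.2% |
| 8 / 2 | 0.667 | 19.1% |

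The result depends only on tau divided by sigma, so it applies equally to FVC in litres.

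**3. The same ending under the AIC rule.** Suppose the random effects are removed and AIC chooses between compound symmetry and spatial power. REML null simulation, N = 123, complete data, 1,000 trials per scenario (Monte Carlo about +/-1.4 points at 5%), Kenward-Roger not applied:

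| tau / sigma | AIC picks compound symmetry | Error after choice |
|---|---|---|
| 3 / 3 | 97% | 7.3% |
| 4 / 3 | 88% | 8.4% |
| 6 / 3 | 22% | 5.9% |
| 6 / 2 | 0% | 7.1% |
| 8 / 2 | 0% | 10.4% |

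A repeat with 400 trials per scenario gave 98%, 85%, 24%, 0% and 0%, with error about 5-11%. In the last two rows the excess comes from spatial power. Used alone without random effects, spatial power missed in both directions: 1.8%, 3.6%, 6.4% and 9.7% at 3/3, 6/3, 6/2 and 8/2 (2,400 trials, incomplete data).

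**4. Endings that approximately hold the level.**

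- Random effects kept, AIC between compound symmetry and spatial power: 3.8-5.4% (800 trials per scenario, +/-1.5 points).
- Unstructured residuals, no random effects (10 parameters, full rank at nominal weeks): 4.3-6.4% over 750-trial runs and 5.8-6.4% over 1,000-trial runs; about 4-7% overall.
- Random intercept and slope with independent residuals: 4.9%, 5.4%, 5.9% and 6.0% at 3/3, 6/3, 6/2 and 8/2.
- Per-participant slopes with Wilcoxon test: 5.1-5.4%.

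The first, third and fourth lines, and the spatial-power figures in step 3, use incomplete data under assumptions: the timing variation of step 1, 10% of spirometry missing, 20% v 30% stopping early, missingness independent of outcome.

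**The case against.** Four counter-arguments have weight.

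- **AIC protects where it matters most.** A reader of the closed-form table might infer that the slope test would run at up to 19% error. The documents do not support that. The SAP has AIC choose among converging structures, and step 3 shows that AIC hardly ever picks compound symmetry where it inflates most. The large figures need it to be the structure actually used, for example because nothing else converges. This stands, and it limits the size of the point.
- **The plainest reading may be harmless.** Removing the random effects from the model as first specified leaves unstructured residuals, which are identifiable at nominal weeks and approximately hold 5%. This stands, but the SAP does not say that this is the intended ending.
- **Text order suggests a sequence.** If residual structures are changed first and random effects are removed last, the first stage holds its level. This stands in part: the order is not stated, and the last step still permits compound symmetry or spatial power alone.
- **The move away from the protocol's Wilcoxon method.** A reader might see an error here. Protocol section 10 defers detailed analyses to a SAP finalised before unblinding, and the SAP states its mixed model openly. Recording the change is housekeeping.

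**Conclusion.** The point holds as a minor one. The specified covariance model is redundant on either time scale, and the compound-symmetry fallback with random effects kept is redundant too. The two responses to non-convergence are unordered and do not identify the final model. Among the permitted endings, some stay near 5% (3.8-5.4% and about 4-7%). Others may not: about 5-11% if random effects go and AIC chooses between compound symmetry and spatial power, and 7-19% if compound symmetry without a random slope is the structure used.

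The error rates rest on assumed variances (slope SD 3-8 points per year, residual SD 2-3 points), because the documents give none; if slopes do not vary, compound symmetry gives 5%. The simulations did not apply Kenward-Roger. A reader might infer that the model will fail to converge, but neither that nor the frequency of any branch is shown. Nor is the trial's main conclusion at risk: Protocol 10.2.2 and 10.4.2 make secondary analyses exploratory, the SAP (Multiple Testing) calls them hypothesis-generating, and the primary logistic analysis does not use this model.

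**What to change.** In the SAP, for FVC slope:

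1. Specify one identifiable model: fixed arm, time in actual weeks, arm-by-time and baseline; random intercept and slope with a 2x2 unstructured covariance; independent residuals; Kenward-Roger. If nominal visits are used instead, specify unstructured residuals without random effects.
2. Number the fallback steps, and state that no ending may use compound symmetry or spatial power alone without a random slope.
3. A final fallback may be the protocol's per-participant slopes with a Wilcoxon test, which accepts off-schedule and early-termination tests. State whether the baseline value enters each regression. Without it, a participant with one post-baseline value has no slope and drops out, contrary to the SAP's Missing Data section.

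An intermediate step could set the intercept-slope covariance to zero and keep the random slope. It gave 4.8-5.9% in the incomplete-data runs, but 6.9% at 6/3 when an intercept-slope correlation of -0.5 was assumed (1,200 trials, +/-1.3 points), so it is not free of risk.

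The cost is wording only. Standard errors will be about 9-50% wider than under compound symmetry without a random slope (1/0.917 = 1.09 to 1/0.667 = 1.50), across the assumed variances. One sentence recording that the mixed model replaces the method of Protocol 10.4.2 is optional.
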